#### **Study Definition of Adverse Event:**

- Any inpatient hospitalization
- Any emergency room admission
- Actual suicide attempt (per reporting guidelines of the WRJ IRB (VINNE)\*\*

Reporting of adverse events: AEs will be reported to the CSR&D DMC and the WRJ IRB (VINNE) at regularly scheduled reviews as designated by each of these entities.

#### **Study Definition of Serious Adverse Event:**

- Actual suicide attempt (per reporting guidelines by the CSR&D DMC)\*\*
- Death, any cause

Reporting of serious adverse events: SAEs will be reported to the CSR&D DMC within 72 hours of the study team becoming aware of the incident. Furthermore, as required by the WRJ IRB (VINNE), serious adverse events will be reported to the WRJ IRB (VINNE) within 5 days of discovery if the event is determined to be both unanticipated AND may be related to the research.

*\*\*In accordance with VHA Handbook 1058.01 and the Common Rule (45 CFR 46. 103(a) and 46. 103(b)), the WRJ IRB (VINNE) has determined that suicide attempts in this study are expected and should be reported as adverse events. However, per the CSR&D DMC's request, we will report suicide attempts as SAE to the DMC.*

[figure not shown]
## Reasons for stopping assigned treatment and follow-up:

The following events will be considered reasons to stop assigned treatment and or follow-up of an enrolled patient: (1) death because the patient would no longer be accessible to study staff; (2) patient requests to withdraw from the study; or (3) the study investigator or the patient's mental health provider request to withdraw the patient from the study because they believe it is in the best clinical interest of the patient. In the event that the patient is assigned to the intervention, we will ask the patient if they are willing to continue with the outcome assessments but respect his/her wishes if he/she chooses to withdraw from the study.

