**Standard Psychiatric Hospital Discharge Care:** Patients assigned to the PEACE intervention as well as the control condition will receive the standard VA hospital discharge care that occurs as part of psychiatric hospitalization. VA current standard psychiatric hospital discharge care includes five core elements. First, patients and their outpatient providers are required to be involved in discharge planning. Second, patients should be offered evidence-based treatments to address their mental health symptoms. Third, the inpatient team should work with the patient to complete a safety plan prior to discharge. Fourth, the inpatient team should arrange two follow-up care visits within 30 days of discharge. Fifth, the inpatient team in conjunction with the SPC assess whether patients are appropriate to be placed on the High Risk for Suicide List. Patients who are placed on the High Risk for Suicide List receive enhanced oversight as outlined in VA policy. More recently, this enhanced care was renamed the Suicide Prevention Pathway. The SPC oversees the following elements of the Suicide Prevention Pathway: 1) The SPC reminds the mental health provider that the patient should be scheduled to be seen four times within the first 30 days following hospitalization; 2) The primary care or mental health provider is expected to tailor the patient's treatment to address his/her unique risk factors for suicide; 3) The SPC places a pop-up flag in the medical record to alert providers of the patient's high-risk status; and 4) The continued need for the patient to remain on the High Risk for Suicide List is reassessed by the SPC every three months. Of note, at the clinical discretion of the inpatient treatment team and the SPC, some patients may be assigned to the Suicide Prevention Pathway but may not meet criteria for the High Risk for Suicide List. Per VA policy, SPCs are not required to provide clinical care.

**Organizing framework for PEACE's Anti-Suicidal Effect:** As shown in **Figure 4** below, based on the 3ST and our pilot data, we hypothesize that PEACE will reduce the risk for suicide after psychiatric

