**Study Design:** As shown in Figure 5, patients allocated to the PEACE intervention will meet with the study therapist prior to discharge. During this visit, they will receive the first intervention visit. The intervention will be delivered in a private office on GE. After discharge, patients will participate in seven regular follow-up contacts with the study therapist over a period of three months in addition to use of the My3 app.

Depending on patient preference, the regular contacts will occur in a private office on the WRJ VAMC campus or the contacts will occur over the phone or VA Video Connect.

- All patients (including patients randomized to PEACE) will have access to standard discharge care. Furthermore, regardless of study assignment, all patients will undergo four outcome assessments including assessment 1 (baseline or study entry, occurs just prior to hospital discharge)(0M), assessment 2 (occurs one month after baseline assessment) (1M), assessment 3 (occurs three months after baseline

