## **Statistical Considerations**

**Statistical Analyses:** To maintain blinding, the statistician who is otherwise not directly involved in the study will conduct the analysis based on the intention-to-treat principle. Below, we have outlined the specific analysis plan for assessing each of the three aims of interest of this study. As part of the analyses of the three aims, we plan to account for potential confounding. We will assess for statistically significant differences in baseline study characteristics, including age, sex, race, history of suicide attempts, mental health diagnosis, marital status, employment, recent life stressors, service history, High Risk for Suicide List status, and Suicide Prevention Pathway status between study arms using *t*-tests for continuous measures and chi-squared tests

for dichotomous variables. We will report these results using 95% confidence intervals (CI) and *P*-values. We will define statistical significance as a *P*-value < 0.05. If we identify any variables for which there are significant differences across study arms, we will control for these confounders in the analysis of the aims.

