### **Risks and Side Effects:**

## **Potential Risks**

As described above, it is expected that patients may report worsening suicidal ideation or suicidal behaviors at the study assessments (i.e., assessments 1, 2, 3, and 4) regardless of whether they are assigned to the intervention or control condition. It is also possible that patients assigned to the intervention arm may report worsening suicidal ideation or suicidal behavior during an intervention visit. It is also possible that patients could be seen in the emergency room or be hospitalized because of any of these events. Thus, it is expected for the patients to continue with the study unless the patient requests to be removed from the study.

Furthermore, as outlined in our **Safety Alert Protocol**, study personnel will immediately follow the safety alert protocol in response to any reports of worsening suicidal ideation or behaviors. If necessary, patients will be connected immediately with required clinical treatment. All patients will continue to have access to standard-of-care treatment during the course of the trial regardless of study assignment. Furthermore, all patients may continue any treatments that they were receiving as part of their routine care prior to enrolling in the study.

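### The request to stay in outcome assessment after withdrawal is written for the intervention arm only, so outcome ascertainment after withdrawal can differ by arm

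*Combined protocol and SAP*

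**What the plan says.** Under Reasons for stopping assigned treatment and follow-up, the protocol begins: "The following events will be considered reasons to stop assigned treatment and or follow-up of an enrolled patient". Three reasons follow: death, the patient's own request, and a third in which "the study investigator or the patient's mental health provider request to withdraw the patient from the study" on grounds of clinical interest. None is restricted to one arm. The next sentence is restricted: "In the event that the patient is assigned to the intervention, we will ask the patient if they are willing to continue". What they are asked to continue is outcome assessment, and a refusal is respected.

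Other sections set follow-up rules without regard to arm:

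- **Study Design:** "regardless of study assignment, all patients will undergo four outcome assessments".
- **Potential Risks,** on worsening ideation or behaviour: "it is expected for the patients to continue with the study unless the patient requests to be removed from the study".
- **Study Population and Recruitment:** reminders are planned for all patients.
- **Subject Compensation:** each completed assessment is paid.

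Statistical Considerations says that the statistician "will conduct the analysis based on the intention-to-treat principle". For the primary outcome, missing data get one sentence naming a maximum-likelihood approach. No sensitivity analysis is stated. Sample Size assumes dropout of at most 10%, as a single figure not split by arm.

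**The concern.** An intention-to-treat comparison needs outcome data collected on the same terms in both arms, including from patients who stop. Here the written step to recover data after stopping exists for one arm. A control patient can ask to leave, or can be withdrawn by a clinician, and the text then directs nobody to ask about the remaining BSS assessments.

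In a trial of suicidal ideation after psychiatric discharge, withdrawal on clinical grounds is plausibly related to the primary outcome. If PEACE withdrawals are partly recovered and control withdrawals are not, the observed arms can differ in composition for a procedural reason. A likelihood analysis copes if missingness depends only on arm and observed scores. It does not cope if missingness depends on scores that were never observed, and the plan includes nothing that would show how much this matters.

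**Working it through.** **1. The provisions side by side.**

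| Step | PEACE | Control |
|---|---|---|
| Can leave at own request | Yes | Yes |
| Can be withdrawn by investigator or provider | Yes | Yes |
| Scheduled for all four assessments | Yes | Yes |
| Reminders, and payment per assessment | Yes | Yes |
| Asked, after stopping, to continue assessments | Yes, stated | Not stated |

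Only the last row differs. The general provisions above it do not say what happens once a control patient has asked to leave or has been withdrawn.

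**2. The plan's own sample size.** Inputs from Sample Size and its Table 3: effect size d = 0.5, power 80%, alpha 5%, correlation 0.5, m = 4 time points. The plan does not state sidedness; two-sided alpha reproduces its figure.

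n per arm = 2(1.960 + 0.842)² × [1 + (m − 1) × 0.5] / (m × d²) = 2 × 7.849 × 2.5 / (4 × 0.25) = 39.24, so 40, as stated.

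Allowing for 10% dropout, 40 / 0.90 = 44.4, so 45 per arm against the stated 46. The figures agree to within one patient per arm. At 10%, the retention rule touches about 46 × 0.10 = 4.6 patients per arm.

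**3. Illustrative bias in raw observed means.** Let w be the share withdrawing in each arm, k the share of PEACE withdrawals retained, and δ the excess BSS score of withdrawals over those who stay. No control withdrawals are retained, and there is no true effect. Then

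false difference (PEACE minus control) = w k δ / (1 − w + w k).

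From the documents: w = 0.10. Assumed: δ = 3 to 8 points, k = 0.5 to 1, and the same w and δ in both arms.

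| k | δ = 3 | δ = 5 | δ = 8 |
|---|---|---|---|
| 0.5 | 0.15 / 0.95 = 0.16 | 0.25 / 0.95 = 0.26 | 0.40 / 0.95 = 0.42 |
| 1.0 | 0.30 | 0.50 | 0.80 |

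Higher BSS is worse, so with δ > 0 the bias runs against PEACE. With δ < 0 it runs in its favour.

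**4. The same on the SD scale.** Take 46 per arm, w = 0.10 and δ assumed at 0.25 to 1.0 SD. Subtract the bias from d = 0.5 and use power = Φ(effect / √[0.625(1/n_P + 1/n_C)] − 1.96), where 0.625 = 2.5/4.

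- **Equal recovery, shown for none in either arm (41.4 per arm observed):** bias 0, power 82%.
- **Half of PEACE withdrawals recovered (43.7 against 41.4):** bias 0.01 to 0.05 SD, power 81% to 74%.
- **All PEACE withdrawals recovered (46 against 41.4):** bias 0.025 to 0.10 SD, which is 5% to 20% of the planned effect. Power is 80% to 66%.

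Steps 3 and 4 treat a withdrawn patient as contributing no scores and make no use of earlier ones. They show scale and do not forecast the hurdle-model result.

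**The case against.** The strongest defence is that the sentence is benign. PEACE patients have eight contacts and an app that they can stop while still being assessed, so the protocol separates stopping treatment from leaving follow-up for them. Controls get standard care alone, as the protocol says: "Patients assigned to the PEACE intervention as well as the control condition will receive the standard VA hospital discharge care". They have no study treatment to stop. The sentence also helps intention to treat by keeping patients who discontinue PEACE. This probably explains the wording, and it is a good reason to keep the request for PEACE. It does not cover the second and third stopping reasons, which concern leaving the study and can arise in either arm.

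Four stronger readings are tempting, and the documents do not support them.

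- **That controls will not be asked.** The text is silent on this; staff may ask them in practice.
- **That unequal missingness and bias are certain.** No dropout by arm is given. PEACE patients have extra contacts from which to disengage, so the request could narrow a gap instead of opening one. Bias also requires missingness that depends on unobserved scores.
- **That the bias could reach 1.0 to 2.4 points.** This needs 20 to 30% withdrawing with every PEACE withdrawal retained, and the top end also needs withdrawals 8 points worse. The plan allows for at most 10%, and no patients dropped out of either pilot. Even the 10% is overall dropout, and patients who are simply lost cannot be asked.
- **That the bias can be set against a planned effect of 2.6 to 4.0 points.** This multiplies d = 0.5 from the 19-patient pilot RCT by SDs of 5.2 to 7.9 from a different, nine-patient pre-post pilot. The plan states no such point effect.

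**Conclusion.** The point holds as a specific, avoidable risk. The written rule is arm-specific where the stopping reasons are not, and no other section supplies the missing step for controls. Followed literally, it can make outcome ascertainment after withdrawal differ by arm, and may bias the BSS comparison if withdrawal depends on unobserved ideation.

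Size and direction cannot be fixed from the documents. Under the stated assumptions, the illustrative false difference is about 0.2 to 0.8 BSS points. If withdrawals are worse, it runs against PEACE and could mask a real benefit; it would not create a false one. If withdrawals are better, the sign reverses. This is a cheap improvement worth making and does not invalidate the design.

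**What to change.** Replace the intervention-only sentence with one rule for both arms. Any patient who asks to withdraw or is withdrawn, or who stops the PEACE contacts, is asked whether they are willing to continue the remaining one-, three- and six-month outcome assessments, and their wishes are respected. Wording the trigger this way gives controls a clear one, since they have no study treatment to stop. It does not change who may be withdrawn or on what grounds.

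Report by arm how many patients were asked, how many continued, and the missingness at each assessment with reasons.

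The cost is one protocol sentence, a few lines of reporting and a few extra calls by existing staff. The planned sample size stays at 92. If staff already ask controls, the edit only records what they do.

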We will calculate 95% CI and *P*-values and will define a *P*-value of < 0.05 to be statistically significant. We will use the maximum likelihood ratio to account for any missing data.

**Specific Aim 2:** The secondary aim of our study is to determine the mechanism by which PEACE exerts its anti-suicidal effect on patients after psychiatric hospital discharge. Based on available evidence, we hypothesize that the intervention plus standard psychiatric hospital discharge care exerts an anti-suicidal effect on patients after psychiatric hospitalization by improving social connectedness and engagement in care after discharge. We will assess this aim by performing the following analyses: First, we will perform an analysis to demonstrate whether there are greater improvements in social connectedness and engagement in care over time in patients assigned to the intervention versus control condition at one, three, and six months after discharge. For continuous variables measuring patient engagement, we will generate descriptive summary statistics (e.g., means and standard errors, medians) and graphical displays for each measure at baseline (assessment 1) and at assessments 2, 3, and 4. Second, using structural equation modeling, we will calculate mean differences in scores for each of our continuous measures at the one-, three-, and six-month assessment periods, as well as the associated 95% confidence intervals and *P*-values. For the categorical measure of patient engagement, we will use chi-squared tests to compare the proportion of patients adhering to their discharge plan between the two study arms at one-month after discharge. Third, we will assess whether social connectedness and patient engagement mediate the effect of the intervention on suicidal ideation, as measured by total BSS scores. In order to conduct this analysis, we will use structural equation modeling. We will use the maximum likelihood to account for any missing data. We will calculate the associated 95% CIs and *P*-values and will define a *P*-value of 0.05 to be statistically significant.

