## **Subject Compensation:**

We will compensate each patient for each study assessment completed. Patients will receive \$25 for the assessment 1; \$50 for assessment 2 (one-month follow-up); \$75 for assessment 3 (three-month follow-up); and \$100 for assessment 4 (six-month follow-up). The maximum total compensation is \$250. We chose this staggered payment schedule for two reasons: First, we are asking patients to remain in the study over the course of six months and we believe that this payment schedule will account for the additional inconvenience and burden on the patient. Second, prior studies have shown that the use of staggered payments and higher compensation improves study retention while not being coercive. Every effort will be made to compensate participants, however, if a participant does not provide necessary information for payment purposes, study staff will initiate the following: In the event that the patient has completed all assessments and/or interventions, and has not provided the necessary information to pay them, study staff will call the patient up to five times to obtain the required information. In addition to these phone attempts, after completion of the study, study staff will mail a blank VA 10091 (Direct Deposit/Vendorization) form with instructions, envelope, and stamp for the patient to easily mail back. After five attempts to contact the patient via phone and one attempt at mailing the patient, if the patient does not provide the necessary information to be paid, we will classify this patient as "unable to be paid".

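### The withdrawal section offers continued outcome assessments to intervention patients and does not say whether withdrawn control patients will be asked

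*Combined protocol and SAP*

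**What the plan says.** The section on reasons for stopping assigned treatment and follow-up opens with one list for both arms: "The following events will be considered reasons to stop assigned treatment and or follow-up of an enrolled patient". The reasons are death, the patient's own request, and a clinical decision in which "the study investigator or the patient's mental health provider request to withdraw the patient from the study". The section then gives its only provision for continued data collection, which applies when "the patient is assigned to the intervention, we will ask the patient if they are willing to continue with the outcome assessments". Control patients are not mentioned.

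Four other places bear on the point.

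- Study Design: "regardless of study assignment, all patients will undergo four outcome assessments". It does not address patients who have been withdrawn.
- Statistical Analyses: the statistician "will conduct the analysis based on the intention-to-treat principle".
- Specific Aim 1: "We will use the maximum likelihood ratio to account for any missing data". I read this as likelihood-based handling of missing scores. No sensitivity analysis for informative missingness is described.
- Potential Risks: it anticipates that "patients may report worsening suicidal ideation or suicidal behaviors at the study assessments" in either arm, and expects such patients to carry on unless they ask to leave. It does not say what follows once a clinician has withdrawn someone.

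**The concern.** An intention-to-treat comparison needs outcomes collected by the same rule in both arms. Here a provider may withdraw a control patient and nothing tells staff to ask about further assessments. For a withdrawn PEACE patient the text does tell them to ask. If the withdrawn patients are those doing badly, high BSS scores could be kept in the PEACE arm and lost in the control arm. The control mean would then look better than it is and the treatment effect would be diluted. The difference in missingness would come from the protocol's wording, not from patient behaviour, so it can be avoided.

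**Working it through.** **The plan's own figure.** Sample Size gives 40 evaluable per arm and 46 recruited, using 80% power, alpha 0.05, effect 0.5 SD, correlation 0.5 and four timepoints. The repeated-measures formula gives

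n per arm = 2(1.960 + 0.842)² × [1 + 3 × 0.5] / (4 × 0.5²) = 39.24, rounded up to 40.

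Inflating for 10% dropout gives 40/0.9 = 44.4, so 45, against the stated 46. The figure reproduces closely, and the point below does not change it.

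**What is assumed.** The documents give no clinician-withdrawal rate. The nine-patient pilot kept everyone, and the 19-patient pilot RCT had no dropouts. All withdrawal counts are therefore assumptions.

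**Simulation.** The setting is 46 per arm, with baseline, month-1 and month-3 scores correlated 0.5 and a true effect of 0.50 SD at each follow-up. The month-3 effect is estimated by maximum likelihood under a normal model, using sequential regressions on earlier scores with equal baseline means. The SD of the estimate is about 0.18. In each arm the k patients ranked worst by a clinician's judgement are withdrawn before month 3. That judgement correlates 1.0 down to 0.5 with the unseen month-3 score, which gives the ranges below. Under the current wording, withdrawn controls are not assessed, and withdrawn PEACE patients stay if they agree.

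| Withdrawn (PEACE, control) | Current, all PEACE agree | Current, half agree | Both-arms offer, half agree |
|---|---|---|---|
| 1, 1 | 0.467–0.484 | 0.483–0.492 | 0.500 |
| 2, 2 | 0.437–0.469 | 0.468–0.485 | 0.500 |
| 2, 1 | 0.467–0.484 | about 0.50 | 0.507–0.514 |
| 2, 0 | 0.500 | 0.515–0.531 | 0.515–0.531 |

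With the offer in both arms and everyone agreeing, every row is 0.500.

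- The largest shift is 0.500 − 0.437 = 0.063 SD, about a third of a standard error. The smallest in the first two rows with all agreeing is 0.500 − 0.484 = 0.016 SD.
- If withdrawals are equal and every withdrawn PEACE patient declines, the estimate is 0.500, so there is no bias to fix.
- If the worsening was scored at month 1 and the patient is withdrawn afterwards, the estimate is also 0.50, because the normal likelihood model uses the earlier score.

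**Cruder check in BSS points.** Suppose the likelihood analysis recovers nothing and the lost controls score g SD worse than the 41 per arm otherwise expected (46 × 0.9 = 41.4). Losing c of them shifts the effect by (c/41) × g. For c = 1 to 2 and g = 0.5 to 1.5 this is 0.012 to 0.073 SD. With the pilot SDs of 5.2 (three months) and 7.9 (baseline) that is about 0.06 to 0.58 points. The protocol treats 5 points as possibly clinically relevant.

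**Logistic part of the planned hurdle model.** If k of 46 controls with ideation are lost and nothing is recovered, the control log odds move by log((46p − k)/(46 − 46p)) − log(p/(1 − p)), where p is an assumed prevalence of any ideation.

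- p = 0.3, k = 2: log(11.8/13.8) = −0.16
- p = 0.7, k = 2: log(30.2/32.2) = −0.06
- k = 1: −0.08 and −0.03 respectively

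The standard error of the arm difference is √(2/(46p(1 − p))), about 0.42 to 0.46 for p from 0.3 to 0.7. The ratio is again at most about a third.

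**The case against.** The strongest reply is that the asymmetry follows from the design. A PEACE patient has contacts and an app that can stop while assessments go on. A control patient receives only standard care, which the study does not deliver, so study participation is essentially the assessments. A control patient who asks to leave has nothing further to be offered. A clinician who withdraws one may mean precisely to stop the assessments. This stands for patient-initiated withdrawal and explains the wording. It does not dispose of clinician-initiated withdrawal, which applies to both arms and need not be directed at the questionnaires.

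A reader might infer that the protocol bars control patients from further assessment, or restricts the offer to PEACE patients in so many words. It does neither; it is silent on controls, and Study Design plans four assessments for everyone. A reader might also see a contradiction with Potential Risks. That section states an expectation about patients who worsen, and it can stand beside the withdrawal section as the operative rule.

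The benefit of the fix is also limited. A safety exemption could cover many clinician-withdrawn controls, so the both-arms column is an upper limit. With two PEACE and one control withdrawn and half agreeing, the fix moves the estimate slightly away from 0.50. With two and none it changes nothing. The largest shift needs two unscored withdrawals per arm, judgement perfectly correlated with the unseen score, and full PEACE agreement. All of this stands, and it limits how much weight the point can carry.

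**Conclusion.** The gap is real but minor. The text gives a retention step for one arm and leaves the other unaddressed, and this matters mainly when the investigator or a provider withdraws a control patient. Under the assumed one or two unscored withdrawals per arm, with all withdrawn PEACE patients agreeing to stay, the effect shrinks by about 0.02 to 0.06 SD.

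The documents do not support a claim that the result would be materially biased or that the intention-to-treat analysis fails. They give no sign that such withdrawals are common. Nor do they support a claim that the rule favours PEACE: with equal withdrawals any shift is toward zero, and an upward shift appears only when more PEACE than control patients are withdrawn and some of them decline.

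The absence of bias for worsening already scored was shown for a normal model. The plan uses a hurdle model and does not state how the repeated assessments are joined, so that result may not carry over exactly. The case for changing the text rests on its low cost, not on a large expected bias.

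**What to change.** In the section on stopping treatment and follow-up, replace the intervention-only condition with one that ignores arm: any living patient who is withdrawn, whether by their own request or by a clinician, is asked about continuing outcome assessments, unless the patient declines or the clinician judges the assessments themselves unsafe. Record stopping study treatment and stopping follow-up as separate events, each with reason, date and arm. Clinicians keep their authority to withdraw patients, and Potential Risks needs at most a cross-reference.

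The cost is a few words and one set of fields on the withdrawal form. Sample size and analysis are unchanged. The extra burden is a few assessments that are already scheduled for every patient and budgeted per visit ("We will compensate each patient for each study assessment completed"). The change removes the arm-specific rule. It will not remove differences caused by unequal withdrawal, and because of the safety exemption it may recover few control scores.
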